## 1.0 SUMMARY

The goal of this study is to obtain user feedback while placing and observing the *DAISY* uterine drain with wall suction. This study defines the obstetrical surgeons as “users” and the patients in whom the drain is placed as “participants.” Participants are pregnant women who are undergoing cesarean delivery (CD), who have not entered active labor, who have consented to drain placement and who have met all the inclusion/exclusion criteria. Users are staff or fellow obstetrical surgeons who will use the drain and provide the evaluation.

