### 4.0 STUDY POPULATION

As described above, this study defines the obstetrical surgeons as “users” and the patients in whom the drain is placed as “participants.” The participants consist of women undergoing planned CD for reasons unrelated to this study. We expect to enroll five (5) obstetrical surgeons of various levels of experience who will each place a drain in one to three participants for a total of 10 participants who are qualified based on the Instructions for Use (IFU) *and* who consent to participation. The following contraindications serve as exclusion criteria.

- Known intrauterine or cervical pathology that would interfere with device placement and/or use
- Ongoing intrauterine pregnancy
- Untreated uterine rupture
- Unresolved uterine inversion
- Current cervical cancer
- Current purulent infection of vagina, cervix, or uterus
- Retained products of conception
- Arterial bleeding requiring surgical or angiographic embolization
- Indication for hysterectomy
- Lack of study consent.

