## **NUMBER OF USERS & PARTIPANTS**

In this study, 5 (five) users will place the *DAISY* drain in ten (10) participants do not have any of the contraindications for drain use at the time of the CD. Each user will place the drain at least once but no more than three times. After each obstetrical surgeon uses the *DAISY* drain, they will be asked to complete a questionnaire (Appendix 1).

The *DAISY* drain and Instructions for Use (IFU) will be evaluated qualitatively for the following including:

- ease of drain placement by obstetrician-surgeon
- appropriate size of drain
- appropriate final location of the deployed drain and incidence of improper placement
- ease of drain connection to suction tubing
- ease of drain removal
- perceived effectiveness of suction
- clarity of the IFU

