### *Consenting:*

The Principal Investigator or research team member may consult a list of eligible patients based on predicted delivery dates. A list of participants who meet/ did not meet eligibility criteria will be maintained in a screening log by the study team. This log will contain identifiable information and is maintained by the team for determining eligibility and data collection purposes. The log also helps the study team to ensure that a participant who declined participation is not approached again upon admission to labor and delivery. IRB approval will be obtained prior to entering data in the screening and enrollment logs. The enrollment log will be a separate log that will contain the key linking participant information with the Participant ID. Each ID will be assigned to participants in a sequential order (e.g., 01-001, 01-002, 01-003....). Participant initials will not be included in the ID. Logs will be stored on password-protected desktops of the study team in a research folder accessible to the study team only. The participant IDs will be used on case report form (CRF) pages and the drain use questionnaire.

The team member will approach potentially eligible patients either in the office or clinic during the pre-operative visit. Patients who initially meet the enrollment criteria will be offered study

participation after a thorough presentation by the study PI, sub-investigator, or research coordinator at the pre-operative visit. At that time, all study risks will be discussed, and the consent form is signed should the patient choose to participate. Some participants may choose to take the consent materials home and return them later.

An updated list of consented participants will be available to the study team along with their participant numbers on a weekly basis. It is expected that at least twice as many participants will be consented as those that meet all inclusion/exclusion criteria at the time of the CD. Enrollment is considered “complete” when all inclusion and exclusion (contraindications) have been fully met

*Drain Placement:*

Described in Section 5

*Drain Removal:*

Described in Section 5

*Data Collection:*

User feedback is collected on a standardized form [see Appendix 1]. Limited participant data will be collected for the purposes of screening and device evaluation. [see Appendix 2] Sonographic images of drain placement may be recorded, printed, and placed in the participant’s study file.

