**VISIT SCHEDULE**

Visit	Visit 1	Visit 2	Visit 3
Procedures	Patient education and consent	Final Enrollment and Drain placement.	Post-partum visit
Timing	Pre-surgical	Drain Placement during CD/ Removal in Recovery Room	4-8 weeks post-partum
Evaluations	Screening using Medical History and current prenatal status	User evaluations Uterine tone assessments Ultrasounds Adverse events	Adverse events
Stipend	No	Yes	Yes

*Participant Stipend:*

Participants will be compensated at a rate of \$100 upon completion of Visit 2 and an additional \$50 for the completion of Visit 3 for a total of \$150.

*Duration of Participation:*

Participants will be considered initially enrolled at the time of consent which may occur a week or more prior to the CD. Participants are expected to be followed for up to the post-partum visit.

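### Participants and the target of ten are counted by completed placements, and nothing records an insertion that is attempted but not completed, so ease of placement can rest on successes only

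*Protocol*

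**What the plan says.** **Definition by placement.** Sections 1.0 and 4.0 both define participants as "the patients in whom the drain is placed as" participants.

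**Definition by consent and eligibility.** The next sentence of Section 1.0 describes them as pregnant women having a cesarean "who have consented to drain placement and who have met all the inclusion/exclusion criteria". Under Consenting in Section 6.0, enrollment is complete "when all inclusion and exclusion (contraindications) have been fully met". Neither requires the drain to be in.

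**Target and limit.** Section 4.0 expects five surgeons "who will each place a drain in one to three participants for a total of 10 participants". The Number of Users section adds: "Each user will place the drain at least once but no more than three times".

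**What is evaluated.** Section 3.0 names ease of placement among the things the sponsor wants to learn. The Number of Users section lists it again, together with "appropriate final location of the deployed drain and incidence of improper placement".

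**What is recorded.** The questionnaire follows each use of the drain. Its header (Appendix 1) asks for placement number 1, 2 or 3. Appendix 2 lists a time of insertion and a time of removal, and nothing on whether an attempt was made, whether it succeeded, or why not.

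**The concern.** The study exists to find out how surgeons get on with inserting this drain. An insertion that has to be abandoned is the most informative single observation it could make. Section 2.0 gives a closed or narrow cervix as the reason for having a drain, and participants have not entered active labor, so a difficult passage through the cervix is a foreseeable event.

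If the definition, the target and the forms all start from a drain that is in place, that event has no assigned status. Ease ratings would then be conditional on success, which biases them toward the device. A later analysis plan could choose a denominator, but it could not recover attempts that were never recorded.

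**Working it through.** **1. The stated number.** The protocol gives no sample-size calculation for the ten. It can only be checked for consistency: 5 surgeons × 1 to 3 placements = 5 to 15 placements, so 10 is feasible.

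**2. Following one case through the text.** Take a consented woman who meets every criterion at the cesarean, but in whom the drain cannot be passed through the cervix.

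| Place in protocol | Her status |
|---|---|
| Definition in Sections 1.0 and 4.0 | Not a participant |
| Second sentence of Section 1.0; Consenting | Participant, enrollment complete |
| Target of ten and limit of three per surgeon | Not counted, since both are in placements |
| Withdrawal of Participants | Not covered: it deals with lost eligibility and self-withdrawal |
| Discontinuation note in Section 5.0 | Not covered: it applies once a drain is in |
| Appendix 1 | No placement number; several items presuppose a drain in place, and there is no not-applicable option |
| Appendix 2 | No field for attempted, placed, or reason not placed |

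The two descriptions of a participant give opposite answers, and no other rule settles it.

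**3. What one to three such cases would do.** The protocol gives no failure rate, so the number of failures k is an assumption. With 10 completed placements there are 10 + k attempts. The intervals are exact (Clopper-Pearson) 95% intervals for the failure proportion k/(10 + k).

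| k | Success per attempt | Failure per attempt (95% CI) |
|---|---|---|
| 0, or failures left out | 10/10 = 100% | 0/10 = 0% (0 to 30.8%) |
| 1 | 10/11 = 91% | 1/11 = 9.1% (0.2 to 41.3%) |
| 2 | 10/12 = 83% | 2/12 = 16.7% (2.1 to 48.4%) |
| 3 | 10/13 = 77% | 3/13 = 23.1% (5.0 to 53.8%) |

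**4. Effect on the ease score.** Section 8.0 scores answers from 1 to 5 and summarizes them mainly by means, medians and standard deviations. Suppose each completed placement scores 4 for ease of insertion and each failure scores 1. The mean is (10 × 4 + k × 1)/(10 + k): 4.00 with failures left out, and 41/11 = 3.73, 42/12 = 3.50 or 43/13 = 3.31 for k = 1, 2 or 3.

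**5. How likely is at least one failure?** For an assumed failure probability p per attempt, the chance of at least one failure before the tenth placement is 1 − (1 − p)^10. The expected number of failures is 10p/(1 − p).

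- p = 5%: 40% chance, 0.5 expected
- p = 10%: 65% chance, 1.1 expected
- p = 20%: 89% chance, 2.5 expected

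**The case against.** The best defense is that exclusion is nowhere stated. The Test Environment section documents each use and the questionnaire follows each use; an attempt may well be a use. The item on ease of insertion through the cervix runs down to strong disagreement, there is space for comments, the sponsor follows up every unfavorable answer, and sponsor staff observe. A failed insertion might therefore come to light. This stands as far as it goes: the gap is a missing rule. It does not remove the gap, because use is undefined and the forms are built around placements.

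A second defense is that analysis sets usually belong in the analysis plan, and that Appendix 2 is a list of primary data, so the case report form itself may hold more. That is fair for the denominator. The participant definition, the questionnaire and the data list, however, are fixed in this protocol.

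Some stronger readings are tempting, and the text does not support them:

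- *Failed insertions are dropped and replaced until ten drains are in.* No section says so.
- *The incidence of improper placement is judged only on successes.* A drain that is deployed but badly located is still placed. Its participant stays in, and the ultrasound assessments of position can show it. Only insertions that were never completed are at risk.
- *Consent and eligibility give conflicting enrollment points.* The Visit Schedule section says "Participants will be considered initially enrolled at the time of consent which may occur a week or more prior to the CD"; with the Consenting text this describes initial and then complete enrollment, which are stages.
- *Half of the consented women have no stated outcome.* The expectation that "at least twice as many participants will be consented as those that meet all inclusion/exclusion criteria" concerns eligibility at the cesarean, for which there is a screening log. It says nothing about failed insertions.
- *A hard insertion could be relabeled as a contraindication.* The criterion in Section 4.0 is limited to known pathology.
- *The study will report 10/10.* No placement-success rate is specified.

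**Conclusion.** The point holds as an inconsistency with a recording gap. Two descriptions of a participant disagree about an eligible woman whose insertion is attempted and not completed, and the target, the limit per surgeon, the questionnaire header and Appendix 2 all follow the placement-based one. Ease of placement can therefore be judged on completed placements only.

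At this sample size one omission is enough to change the message: about 9 percentage points on success per attempt, and about 0.3 points on the mean ease score. Both sizes rest on assumed numbers of failures and assumed scores; the true failure rate is unknown and could be zero. The study is descriptive, so no test or error rate is affected. It should be corrected before enrollment, because the information cannot be reconstructed reliably afterwards.

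**What to change.** - Define the evaluation set as every consented, eligible woman in whom insertion is attempted, say when an attempt begins, and align Section 1.0, Section 4.0 and the Number of Users section with it.
- State that a use includes an attempt that is not completed. Require the case report form and at least the insertion items of the questionnaire for every attempt, and number the questionnaire by attempt.
- Add three fields to Appendix 2: attempted (yes/no), placed (yes/no), and reason not placed.
- Report placed/attempted beside the ease ratings.
- State whether a failed attempt counts toward the ten and toward the limit of three per surgeon. Recruitment may still run to ten placements, provided failed attempts stay in the denominator.

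This needs edits to three sections and a few form fields, with no added procedures. The small downside is that the placement result may look less favorable.

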## 2.0 BACKGROUND AND RATIONALE FOR STUDY

Postpartum hemorrhage (PPH) is the leading cause of maternal mortality worldwide. (D’Alton 2020). It is estimated that 14 million cases of PPH occur each year worldwide (Rath, 2011). In the United States, PPH causes up to 12% of maternal deaths and is the leading cause of death occurring on the day of delivery (ACOG 2017; Butwick 2019; Evensen 2020; Hawkins 2020). According to the American College of Obstetricians and Gynecologists (ACOG), between 54% and 93% of PPH-associated mortality may be preventable while 70-80% of PPH is due to abnormal uterine tone (atony) (ACOG 2017). Atony involves a deficient response to physiological signals that promote uterine contraction and blood vessel compression after delivery. Contraction of the myometrium compresses the blood vessels supplying the placental bed and thereby causes mechanical hemostasis. Uterine atony following CD is a relatively common problem in the non-laboring patient because contraction of the myometrium is almost entirely absent. Restoring uterine tone can be addressed through 1) medication, 2) surgery, or 3) mechanical means. Mechanical restoration of uterine tone includes the use of a tamponade balloon (Hawkins 2020; ACOG 2017, or Bakri® Balloon, Cook Medical, Bloomington, IN). This technique is counterintuitive since it involves outward pressure on the uterus when the actual goal is uterine contraction (D’Alton 2020). Additional devices have employed the use of suction (Jada®, Organon, Inc., Jersey City, NJ).

Post-partum unrecognized uterine hemorrhage due to a closed or narrow cervix that allows blood to collect in a patient undergoing a CD could lead to complications such as dangerously low blood pressure. Providing a conduit for blood to escape via a uterine drain was the basis for developing the *DAISY* Drain. The *DAISY* drain is intended to provide a channel through the cervix for fluid drainage after pelvic surgery. As of September 2023, this device has been deemed “exempt” from the 510(k)-clearance process by the U.S. Food and Drug Administration (FDA). In this study, we wish to use the drain as intended in a small number of subjects but add low-level suction (similar to the Jada device). Briefly, the drain is inserted through the hysterotomy after removal of the placenta and guided down through the cervix and the vagina during the surgery, the distal end of the drain is connected to standard wall suction which establishes a vacuum causing the uterine walls to contract, producing a tamponade of the bleeding vessels and restoring uterine tone. Simultaneously, the suction removes any blood that has collected after closure of the hysterotomy, and the quantity of blood removed can be easily measured by viewing the suction canister. Device evaluation in a small population of appropriate participants is proposed below.

### 3.0 OBJECTIVES

This is a device evaluation study in 10 women who are undergoing a planned CD or non-emergent CD. Obstetrical-surgeon use of the technology in the operating room provides the Sponsor with the important information on how the intended user population interacts with the drain, ease of placement, and effects of adding suction during a clinical case. Further, the Sponsor wants to test the accuracy of the Instructions for Use document.

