## **6.0 STUDY DESIGN AND METHODOLOGY**

This is a prospective, single-arm, device evaluation study of five (5) obstetrical surgeons placing the drain with low-level suction in ten (10) women undergoing elective, non-emergent cesarean delivery.

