## **METHODS**

### *User Training:*

Minimal product training is necessary other than a review of the IFU. Company personnel will initially observe the insertion and removal procedures and secure feedback post placement and removal to be sure that the IFU is clear and appropriately informative.

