#### *Sponsor Responsibilities*

- a) Assure IRB approval of protocol and informed consent is obtained
- b) Select and train Monitors as needed
- c) Select Sites and Investigators
- d) Train Investigators in device use
- e) Obtain curriculum vitae and proof of appropriate licensure of Investigators and study staff
- f) Control shipment of devices
- g) Investigate device-related adverse events
- h) Maintain responsibility for data review and analysis
- i) Obtain statement of financial disclosure for publication and presentation purposes

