**APPENDIX 1**  
**DEVICE USE QUESTIONNAIRE**

Surgeon Name: \_\_\_\_\_

Obstetrician

Fellow

Resident (Circle one)

Years of experience in Obstetrical Surgery: \_\_\_\_\_

Date of Evaluation: \_\_\_\_\_ Placement #: 1 2 3 (Circle One)

Type of Suction Tube used (Brand & ID): \_\_\_\_\_

This Questionnaire aims to evaluate a set of aspects related to the use of the Daisy® device by the personnel in attendance. You are asked to indicate your level of agreement for each of the questions posed below, according to the scale of responses, place a check mark in the appropriate box.

	Strongly Agree	Agree	Neutral	Disagree	Strongly Disagree
Device training clearly explained insertion, use and removal of the device.					
The Instructions for Use (IFU) are clear and concise.					
The Daisy was easy to insert through the cervix.					
The Daisy was easy to properly position within the uterus.					
The Daisy was easily visualized in the lower uterine segment at time of placement.					
The Tube of the Daisy was easily advanced through the vaginal canal.					
The Cap of the Daisy was easily identified & retrieved outside the introitus.					
The Cap of the Daisy was easy to remove from the Tube.					
The Cap of the Daisy had adequate retention in the Tube.					
The Daisy did not interfere with the closure of the hysterotomy incision.					
The Daisy Tube fits easily into standard suction tubing.					

The suction tubing was easy to secure to the leg of the participant using the provided adhesive Catheter Anchors.					
The Daisy remained in place until elective removal.					
The estimated blood loss from the uterus was easy to determine.					
Use of the Daisy did not interfere with routine OR or PACU practices.					
The force to remove the Daisy was acceptable.					
Overall, the Daisy was easy to use.					
The Daisy drained without intervention (clot removal). Describe any clots or interventions in the Comments below.					
Blood flow was easy to visualize through the Tube.					
Overall, the Daisy met all the user needs as intended.					

Other comments regarding the use of the Daisy: \_\_\_\_\_

\_\_\_\_\_

\_\_\_\_\_

\_\_\_\_\_

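### The protocol sets out to test the accuracy of the Instructions for Use, but no planned measure addresses accuracy; the forms ask only whether they are clear

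*Protocol*

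**What the plan says.** Section 3.0 (Objectives) adds an aim for the IFU to those on placement and suction: "Further, the Sponsor wants to test the accuracy of the Instructions for Use document".

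The parts of the protocol that would serve that aim are these:

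- **Section 6.0, number of users and participants.** The list of what will be evaluated includes "clarity of the IFU". Accuracy is not on the list. On repeat use: "Each user will place the drain at least once but no more than three times".
- **Section 6.0, User Training.** Little training is foreseen beyond reading the IFU. "Company personnel will initially observe the insertion and removal procedures and secure feedback post placement and removal"; the stated purpose is an IFU that is clear and tells the user enough.
- **Section 8.0.** Answers are scored 1 to 5 and summarised descriptively. The sponsor follows up any answer of disagree or strongly disagree.
- **Section 10.0, Sponsor Responsibilities.** The list includes "Train Investigators in device use".
- **Appendix 1.** Of 20 statements, one names the IFU: "The Instructions for Use (IFU) are clear and concise". A separate statement rates training: "Device training clearly explained insertion, use and removal of the device". The form records whether the placement is the user's first, second or third.
- **Appendix 2.** The participant data have no field for a departure from the IFU or for assistance given.

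**The concern.** Clarity and accuracy are different properties. A document can be short and readable and still give a step wrongly, omit one or put two in the wrong order. The objective names accuracy, while every planned question about the IFU concerns readability or how informative it is.

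The follow-up rule does not close the gap. A user who found the text clear but had to depart from it at one step can honestly tick agree, and then no follow-up is triggered.

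User evaluation is the main output of this study, as Section 6.0 (Test Environment) makes plain. A favourable mean on the single IFU item could be reported as meeting the accuracy objective when it says nothing about accuracy. A later analysis plan could not repair this, because the information would not have been collected. There are only ten placements, and a surgeon's first use cannot be repeated.

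**Working it through.** The protocol gives no figure for the IFU objective, so there is none to reproduce. The check compares the objective with the measures, and then counts the forms.

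**1. Does any measure address accuracy?**

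| Source in the protocol | What it captures | Tied to an IFU step? |
|---|---|---|
| Section 6.0 evaluation list | Clarity of the IFU | No |
| Section 6.0 feedback to company staff | Whether the IFU is clear and informative enough | Not specified |
| Appendix 1, IFU statement | Clear and concise | No |
| Appendix 1, statements on insertion, positioning, cap, tubing, removal force | Ease or adequacy of the device at that step | No |
| Appendix 1, free text | Comments on use of the device | No |
| Section 6.0 and Appendix 2, placement and ultrasound position | Whether the drain was in the right place | No |
| Section 8.0 follow-up | Reasons for negative answers | Only if the user disagrees |

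No row asks whether a user who followed the IFU as written could complete a step, or whether a step was wrong or missing. A misplaced drain is not attributed to the IFU rather than to technique. A correctly placed drain does not show that the IFU was followed.

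**2. How many forms come from a first use?**

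Inputs: "This is a prospective, single-arm, device evaluation study of five (5) obstetrical surgeons placing the drain with low-level suction in ten (10) women" (Section 6.0), one to three placements per user (Section 6.0), and one questionnaire after each use (Section 6.0).

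- The possible splits of 10 placements over 5 users are 2-2-2-2-2, 1-2-2-2-3 and 1-1-2-3-3.
- Each user has exactly one first use, so first uses = 5 under every split.
- Repeat uses = 10 − 5 = 5, which is 5/10 = 50% of forms.

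**3. What can five first uses show?**

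Let p be the share of first-time users affected by an IFU problem. The protocol gives no such rate, so the values of p are assumptions. The chance of seeing the problem at least once in n independent uses is 1 − (1 − p)^n.

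| p (assumed) | n = 5 | n = 10 |
|---|---|---|
| 10% | 1 − 0.9^5 = 41% | 65% |
| 20% | 1 − 0.8^5 = 67% | 89% |
| 30% | 1 − 0.7^5 = 83% | 97% |
| 50% | 1 − 0.5^5 = 97% | 99.9% |

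If no problem is seen, the one-sided 95% upper bound on p is 1 − 0.05^(1/n): 45% for 0 of 5 and 26% for 0 of 10. The n = 10 figures would need ten independent first-time users, which this design does not have. These probabilities also assume that a problem, once met, is recorded, and the current forms do not ensure that.

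**The case against.** The strongest reply is that the protocol has several routes by which an IFU error could surface. Company staff watch insertion and removal and collect feedback, and Section 9.0 also has sponsor engineers observing users. Appendix 1 rates ease at most steps and has a comment field, misplacement is assessed, and negative answers are followed up. This stands in part. It rules out the reading that the objective cannot be met at all. It does not supply an accuracy measure, because none of these routes is linked to the IFU text and no log is specified.

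A reader might also infer that sponsor training and company staff contaminate the ratings, so that perhaps none of the ten forms reflects use from the IFU alone. The documents do not support that. Staff are said to observe, not to coach. Section 5.0 (drain removal) speaks of a user trained on the IFU, and the training duty in Section 10.0 and the training statement in Appendix 1 can both be read as that same training. Influence from training or prompting is possible but not established, and a contradiction about training is not shown.

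Further, an experienced user can judge whether the IFU is correct, perhaps better than a novice. This stands. The 5 of 10 repeat forms bear on whether a first-time user can work from the IFU alone. They do not measure how far the accuracy objective fails, and repeat use need not push ratings upward. First uses can already be separated by placement number, so no defect is claimed there.

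Lastly, the IFU aim is an added one in a small descriptive study with no pass mark. That limits the weight of the point but does not remove the mismatch.

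**Conclusion.** The point holds in a limited form: the stated accuracy objective has no matching measure. None of the 20 statements in Appendix 1 and no field in Appendix 2 asks whether an IFU step was wrong, missing or departed from, so a high score on the one IFU statement would not show accuracy. Problems may still come to light incidentally.

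Of the ten forms, 5 come from first uses and 5 from repeat uses. This assumes five users, ten completed placements and a form for each. The detection probabilities rest on assumed problem rates and only illustrate how little five first uses can exclude.

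It would go too far to conclude that the IFU is inaccurate, since the IFU is not part of the protocol text reviewed, or that training or prompting has invalidated the ratings. The change is worth making before enrolment because the gap lies in the data-collection forms.

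**What to change.** 1. Add to Appendix 1 an item such as: *Following the IFU as written, I completed insertion, connection/suction and removal without other instruction.* Add an open question: *List any IFU step that was wrong, missing or out of order.* All users should answer at every placement, since experienced users can also spot errors.
2. Have the company observers who already attend note, by IFU step, any assistance given and any departure from the IFU.
3. List the IFU responses by placement number, with first placements shown separately. The form already records the number.
4. If items 1 and 2 are not added, reword the objective in Section 3.0 from accuracy to clarity of the IFU, to match Section 6.0 and Appendix 1.

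The cost is a slightly longer form and a brief log, with no change to sample size or clinical procedure. The one drawback is that a conclusion about first use rests on five uses, and the report should say so.
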